7 STATISTICAL METHODS

7.1 INITIAL DATA EXAMINATION

For each variable of primary and secondary interest (i.e., perceived stress, brooding, optimism, sleep disturbance, and loneliness) and at each time point, we will create histograms and boxplots to examine each variable for normality and outliers. We will then calculate descriptive statistics for each criterion (i.e., mean, median, standard deviation, IQR, range) as well as appropriate frequency statistics for demographic covariates. As a sensitivity analysis, we will repeat the primary statistical models after excluding participants who failed at least three attention checks, as outlined in the protocol paper.

7.2 PRIMARY STATISTICAL MODELS AND ASSUMPTIONS

Repeated measures data, particularly with relatively high amounts of attrition (i.e., missing data in the criterion), are effectively analyzed via multilevel modeling (MLM)¹. MLM has several advantages over traditional approaches, such as repeated measures (rm) ANOVA, the first of which is that rmANOVA assumes constant variance across treatment condition. Secondly, rmANOVA assumes sphericity (the within subject association between individual scores is equivalent across treatment conditions).

The MLM will be computed in R statistical software (R Core Team, 2022) and the *lme4* package (Bates et al., 2015) using REML estimation. Upon running the full model (see below), we will test the key MLM assumptions by examining residuals for linearity, normality, and homogeneity (Raudenbush & Bryk, 2002). We will also examine correlations between random and fixed effects. A significant correlation would violate the assumption of endogeneity, meaning that we would need to consider alternative approaches (McNeish & Kelley, 2019). The full MLM is depicted mathematically as follows (excluding age, gender, and race covariates),

$$PSS_{ti} = \gamma_{00} + \gamma_{01} \text{Condition}_i + \gamma_{10} \text{Time}_{ti} + u_{0i} + u_{1i} + r_{ti}$$

where t denotes repeated observations, i denotes unique individuals, γ_{00} denotes the grand mean of the outcome (fixed intercept), γ_{01} denotes the fixed effect of treatment condition (a Level-2 variable), γ_{10} denotes the fixed effect of time (a Level-1 variable), u_{0i} denotes a random intercept, u_{1i} denotes a random slope for time (allowing each individual to have a unique trajectory), and r_{ti} denotes residual error.

The first MLM will include a random intercept and no random slope. We will then compute the model with the random slope included (see the above equation) and conduct a likelihood ratio test using deviance statistics. If the difference in deviance is significant, we will conclude that the model with the random slope fits the data best. We will also create spaghetti plots to depict random effects in each criterion variable.

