#### **e. Design and Proposed Statistical Analysis**

**I. Changes in Stress and Secondary/Exploratory Outcomes:** To assess whether changes in participants' perceived stress differed across the two groups, we plan to conduct a 2 (group: intervention vs. control) x 4 (time: baseline, 4 weeks, 8 weeks, 12 weeks) repeated-measures ANOVA on participants' PSS scores, controlling for participant age and gender. Similar analyses will be conducted on secondary and exploratory outcome measures. To determine whether usage predicted changes in these outcomes, we will also conduct regression analyses among participants in the intervention condition regressing their scores on each outcome variable onto the number of activities completed within the Happify for Teens platform, while controlling for corresponding baseline scores on that outcome.

ii. **Rumination as a Potential Mediator:** To test whether any observed changes in perceived stress can be attributed to changes in brooding, we also plan to conduct mediation analyses using Hayes' PROCESS macro for SPSS.

iii. **Data Exclusion:** Because careless responding is problematic with online surveys and may artificially increase relationships between variables, we plan to use two separate a priori mechanisms for identifying low quality data: (1) failing 3 or more attention checks in an assessment, and (2) completing an assessment at a rate faster than 1 second per item. We will then re-run the analyses described above without these participants to test whether effects differ when removing low quality data.

iv. **Happify Scale Validation:** To validate the scale for internal purposes, we will conduct confirmatory factor analysis testing the two-factor structure of the scale, and examine convergent validity by computing correlations between the positive emotion subscale and the PANAS-C-S and between the life satisfaction subscale and the SLSS that are collected at baseline.

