### III. RECRUITMENT

a. **Study Population:** This study will recruit adolescents aged 13-17 (Target  $N=800$ ) by advertising to parents on social media (e.g. Facebook, online forums, word of mouth etc...) and existing Happify users who have previously indicated they are parents of adolescents as part of the Happify onboarding process. We will also use a snowballing recruitment method, in which parents who complete the prescreener will be encouraged to share the study with others. We will continue recruiting until 800 participants have met inclusion criteria, successfully completed the baseline assessment, and have started the study.

b. **Inclusion Criteria:** Participants are those who are 13-17 years old, are located in the United States, are a new user of Happify, willing and able to complete the study activities, agree to potentially being selected for the waitlist comparison, agree to not discuss the study with friends or family, report elevated levels of perceived stress (PSS score of at least 14) and rumination (RRS-Brooding score of at least 10), and have a

parent who is willing to consent to the study. Participants are required to complete and pass the baseline assessment to be included in this study.

**c. Exclusion Criteria:** Participants may withdraw from the study or skip assessments at any time; however during the prescreening and/or baseline process, potential participants will be disqualified if they indicate:

- i. They are not 13-17 years old.
- ii. They reside outside of the United States
- iii. They have previously registered for or used Happify
- iv. They are not willing and able to complete the study activities
- v. They indicate that they are not willing to continue the study or refrain from downloading Happify if selected to be on the waitlist
- vi. They are not willing to use a mobile app or internet website
- vii. They do not agree to refraining from discussing the study with friends or family
- viii. They have a PSS score of below 14
- ix. They have an RRS-Brooding score of less than 10
- x. They do not agree to be contacted
- xi. Their parent does not consent to the study
- xii. Participants will also be excluded if they do not complete the baseline assessment, or if they do but fail at least 7/7 attention checks.

2. **Sample Size:** We will recruit 800 participants to be in this study, 400 in each condition.

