6 HANDLING OF MISSING DATA AND OTHER DATA CONVENTIONS

Missingness will be evaluated using standard procedures when analyzing repeated measures data (van Buuren, 2018). First, missingness codes will be created that correspond with the variables in which data points are missing. A series of variables will be created that indicate missingness in each outcome at each measurement time point. We will then explore the extent to which various demographic markers and other variables in the dataset associate with missingness through a series of correlation tests. This practice will ultimately help us determine auxiliary variables for our models.

When working with missing data, there are two “gold standard” approaches to mitigating bias: multiple imputation and full information maximum likelihood (ML) estimation. However, as will be detailed below, multilevel modeling benefits from the fact that the approach does not assume that each group or cluster is balanced. In other words, even if individual A only has a baseline, but individual B has all four observations, no assumptions are violated, and the model will be unbiased (Raudenbush & Bryk, 2002). Thus, multilevel modeling allows us to avoid using a traditional missing data approach by simply harnessing the model’s extant capabilities. Given that we do not anticipate any significant missing data in the predictors or covariates, we plan to use restricted maximum likelihood (REML) estimation in the multilevel framework to account for missing outcome variable data. Final models will be run with identified auxiliary variables included as covariates.

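### SAP 7.2 drops repeated-measures ANOVA over equal arm variances and sphericity, but its own model keeps or only partly relaxes both, and its restricted covariance weakens the missing-data claim in SAP 6

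*SAP*

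**What the plan says.** The protocol (II.e) plans a group by time analysis of PSS, with "time: baseline, 4 weeks, 8 weeks, 12 weeks) repeated-measures ANOVA". SAP 7.2 replaces it with a multilevel model fitted in lme4 by REML. It gives three reasons:

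- attrition: repeated-measures data, "particularly with relatively high amounts of attrition (i.e., missing data in the criterion), are effectively analyzed via multilevel modeling";
- equal arm variances, named ahead of sphericity: "the first of which is that rmANOVA assumes constant variance across treatment condition. Secondly, rmANOVA assumes sphericity";
- sphericity, with this definition: "rmANOVA assumes sphericity (the within subject association between individual scores is equivalent across treatment conditions".

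The printed model has one residual term, and one random intercept and one random slope common to both arms. "The first MLM will include a random intercept and no random slope"; the slope is kept only if a likelihood ratio test is significant. Residuals will be examined for homogeneity, but no remedy is named if they fail.

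On missing outcomes, SAP 6 says that unequal numbers of observations per person violate nothing and leave the model unbiased. "Thus, multilevel modeling allows us to avoid using a traditional missing data approach". Auxiliary variables associated with missingness are added as covariates.

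The protocol (II.a) requires the PSS threshold to be met at prescreen and again at baseline, before randomisation. The exclusion list (III.c) reads "They have a PSS score of below 14". SAP 5 makes baseline PSS one of the four modelled outcome occasions.

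**The concern.** A reason for changing the analysis should describe something the new analysis delivers. Here one of the two criticised assumptions is carried over whole, and the other is relaxed only if the slope is retained.

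The practical stake is missing data. A likelihood analysis handles outcomes missing at random by predicting the unseen visits from the seen ones, using the fitted within-person covariance. If the covariance has the wrong shape, the predictions are off. If dropout depends on scores differently in the two arms, the error does not cancel and appears as an arm difference. SAP 7.2 itself expects attrition to be high.

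**Working it through.** The documents give no SD, correlation, retention or power figure for this point, so there is nothing to reproduce. Every numerical input below is an assumption except the cut-off of 14, the four visits and 400 per arm (protocol III).

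**1. What each version implies.** Let τ00 and τ11 be the random intercept and slope variances, τ01 their covariance and σ² the residual variance, all common to both arms.

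- Random intercept: Var(t) = τ00 + σ², every covariance is τ00, and Var(Yt − Ys) = 2σ² for every pair. This is compound symmetry.
- Random slope: Var(t) = τ00 + 2tτ01 + t²τ11 + σ². Because τ11 cannot be negative, this curve is flat, straight or bends upwards. It cannot jump once and then level off.
- Neither version lets a variance differ by arm.
- Sphericity means equal Var(Yt − Ys) over pairs of visits. It is not equality across arms.

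**2. What the cut-off does over time.** With mean 16, SD 6, constant correlation 0.5, cut at 14 on both occasions and complete data:

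| Variance at week | 0 | 4 | 8 | 12 |
|---|---|---|---|---|
| True | 17.6 | 29.3 | 29.2 | 29.3 |
| Random intercept | 26.3 | 26.3 | 26.3 | 26.3 |
| Random slope | 22.5 | 24.8 | 27.5 | 30.6 |

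The week-8 to baseline ratio is 29.2/17.6 = 1.66. Over means 16-22, SDs 6-7 and correlations 0.5-0.7 it runs from 1.14 to 1.87 (constant correlation) and from 1.28 to 2.11 (decaying).

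**3. What the cut-off does not do.**

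- Arms: both are cut alike before randomisation. The simulated arm variance ratio is 0.998-1.002 at every visit.
- Sphericity: if the cut removes a share δ of baseline variance and the correlation is a constant ρ, Var(Yt − Y0)/Var(Yt − Ys) = 1 − δ(1 − ρ)/2. Take mean 18, SD 6.5 and a whole-number score of at least 14 at baseline. The standardised cut is (13.5 − 18)/6.5 = −0.69, so λ = φ(0.69)/Φ(0.69) ≈ 0.416 and δ = 0.416 × (0.416 + 0.692) ≈ 0.46. With ρ = 0.6 the ratio is 1 − 0.46 × 0.4/2 ≈ 0.91. The Greenhouse-Geisser epsilon stays at 0.990-0.999 when the cut is the only cause.
- Complete data: the cut alone gives a type I error of 0.040-0.050, slightly conservative.

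**4. Why dropout changes this.** In the same example, in units of σ², baseline variance is 0.54 and follow-up variance is 1 − 0.36 × 0.46 = 0.834. Covariances are 0.6 × 0.54 = 0.324 with baseline and 0.6 − 0.36 × 0.46 = 0.434 between follow-ups. The true slope of a follow-up score on baseline is 0.324/0.54 = 0.60. The random-intercept model uses average covariance over average variance: [(0.324 + 0.434)/2] / [(0.54 + 3 × 0.834)/4] = 0.379/0.761 ≈ 0.50. It therefore under-corrects for who left.

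**5. Size under dropout.** Simulation with no treatment effect, mean 18, SD 6.5, cut at 14 twice and a separate mean for each arm and visit. Dropout depends on the last score in opposite directions by arm, with 48-53% retained at week 12.

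| Constant correlation 0.6 | Largest false arm differences (PSS points) |
|---|---|
| Random intercept | −0.22 (week 8), −0.32 (week 12) |
| Random slope | −0.17 (week 4), +0.23 (week 12) |
| Unstructured | at most 0.02 |
| All three, no cut-off | within 0.03 |

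Here the cut-off alone creates the bias. If correlation also decays, the random intercept reaches −0.41 at week 8. Steep decay takes the random slope to +0.59 to +0.83 at week 12, but decay without any cut already gives up to 0.56, so that excess should not be put down to the cut-off. Unstructured stays near 0.01.

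**6. In error-rate terms.** With a false difference d and an assumed SE of 0.5, type I error is Φ(−1.96 + d/SE) + Φ(−1.96 − d/SE). For d = 0.2 (0.4 SE) this is about 7%; for d = 0.4 (0.8 SE), about 13%.

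**7. Shared arm variances.** Equal numbers give no distortion. With a variance ratio of 2 and 200 against 320 completers, the pooled variance is (200 × 2 + 320)/520 = 1.385. The model variance is 1.385 × (1/200 + 1/320) = 0.01125 and the true variance 2/200 + 1/320 = 0.01313. The SE ratio is 0.926 and type I error about 7.0%. A ratio of 1.5 with 240 against 320 gives 5.7%.

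**The case against.** The strongest reply is that the switch rests mainly on attrition and unbalanced data, and that reason stands: the multilevel model uses incomplete participants. SAP 6 also adds auxiliary covariates, and SAP 7.2 checks residual homogeneity. The random slope, if selected, does relax sphericity; in simulated trials at N = 300 and 800 the test selected it in 79-100%, and a linear-slope test then stays near 5%. The bias figures need score-dependent dropout that differs by arm, which the documents neither state nor exclude, and 0.4 points is only 0.4/6.5 = 0.06 SD. All of this stands and limits the point. It does not remove it, because both versions are biased at individual visits when such dropout occurs, so choosing between them is no protection.

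A reader might infer that the entry cut-off itself violates equal arm variances and sphericity by design. The documents do not support that: the cut comes before randomisation, and its effect on sphericity is trivial (step 3). Nor does the missing Time factor on u_1i show that a constant-variance model is intended, since the text beneath the equation defines the term as a slope for time. That is a notation slip.

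The threshold is itself uncertain. The protocol prints 10 or more for PSS at prescreen (II.a) and at least 14 under eligibility (III.b), while SAP 4 says above 14. These must be reconciled; 14 on both occasions is assumed here.

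**Conclusion.** The point holds in limited form. The two assumption-based advantages in SAP 7.2 are wrong as written: equal arm variance is retained, sphericity is tightened or only partly relaxed, and its definition is incorrect. The unbiasedness statement in SAP 6 is too strong, because under missing at random it needs a correctly specified within-person covariance, and the cut-off produces a variance step that neither version fits.

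Under the stated assumptions the cost is a false arm difference of about 0.2-0.4 PSS points at a visit, against about 0.03 or less with an unstructured covariance. With complete data, or dropout that does not differ by arm, it is negligible. Separately, if correlations decay and the random-intercept model were kept, complete-data type I error for a linear arm-by-time term would be 0.079-0.105; that comes from the decay and not from the cut-off. The change is worth making because it is specific and cheap, not because a large error has been shown.

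**What to change.** In SAP 7.2, replace the choice between random intercept and random slope with an unstructured 4 x 4 within-person covariance, fitted by REML in mmrm or nlme::gls, with Satterthwaite or Kenward-Roger degrees of freedom where the software offers them. Let the covariance differ by arm as an option or a sensitivity analysis.

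In the text:

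- define sphericity as equal variances of differences between visits;
- remove or restate the two assumption-based advantages, keeping the attrition reason;
- in SAP 6, say that estimates are unbiased under missing at random with a correctly specified model;
- if the random slope stays as a secondary fit, write it as u_1i x Time.

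The cost is SAP wording and a different R call. The model carries 10 covariance parameters (20 by arm) in place of 2-4. That is minor at the planned 400 per arm, less so for the arm-specific version if retention is poor. An unstructured covariance does not protect against dropout that depends on unseen scores.

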**d. Nature of Study:** The nature of this study is confirmatory and exploratory. We will be testing the hypothesis that using the Happify platform will result in greater decreases in perceived stress and rumination over an 8-week period compared to a waitlist control, with users who complete more activities experiencing more improvement. We also aim to explore the effects of Happify on several factors, including: sleep disturbance, loneliness, and optimism. To do this, we will employ a longitudinal randomized design. Participants will be randomly assigned to either the Happify experimental condition or the waitlist control condition after meeting inclusion criteria and taking a baseline assessment. Those in both conditions will be asked to complete assessments at 4 weeks (mid-point), after the 8-week intervention period (immediate post-test), and 1-month post intervention. Participants will be adolescents aged 13-17 with elevated levels of rumination and stress who are recruited online.

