3 ANALYSIS OBJECTIVES

The primary objective of this study is as follows:

- Comparing the Happify for Teens condition and the waitlist control groups, examine changes in perceived stress and rumination (brooding) across baseline, 4-weeks, 8-weeks (post-intervention), and 12-weeks.

The secondary objective of this study is as follows:

- Comparing the Happify for Teens condition and the waitlist control groups, examine changes in loneliness, optimism, and sleep disturbance across baseline, 4-weeks, 8-weeks (post-intervention), and 12-weeks.

The exploratory objectives of this study are follows:

- Determine the extent to which brooding mediates the relation between treatment condition (Happify for Teens vs. control) and perceived stress.
- Among those in the Happify for Teens treatment, we will explore the extent to which app usage (i.e., number of activities completed, number of active days) associates with each of the five outcome variables from the primary and secondary objectives.

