5 ENDPOINTS AND COVARIATES

The primary criterion of interest will be perceived stress scores, self-reported at baseline, 4-week midpoint, 8-week post, and 12-week follow-up. The secondary criterion of interest will be brooding scores at the same time points. Additionally, three exploratory outcomes will be examined at the same time points: optimism, sleep disturbance, and loneliness. The effect of the Happify treatment will be examined for each outcome.

In each model, we will covary the effects of participant age, gender, and race. Gender will be coded into two binary variables (0 = man or other, 1 = woman; 0 = woman or man, 1 = other). Race will be coded into a single binary variable (0 = White, 1 = all other races). Given that individuals who identify as White comprise almost 75% of the sample, this coding scheme prevents saturating each model with a large number of dummy codes while still preserving much of the racial distribution of the sample.

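### The SAP's primary model has no condition-by-time term, so its one treatment coefficient averages the arm difference over all four visits, pre-randomisation baseline included, and does not test the hypothesised greater fall in stress.

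*SAP*

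**What the plan says.** SAP section 7.2 presents the primary model with the words "The full MLM is depicted mathematically as follows (excluding age, gender, and race covariates". The fixed part is an intercept, one Condition coefficient (γ01) and one Time coefficient (γ10). A random intercept, a random slope and residual error follow. The definitions below the equation name the same terms and no interaction, so a term lost in text conversion is unlikely. The SAP says that γ01 "denotes the fixed effect of treatment condition (a Level-2 variable", so it takes one value per participant for the whole trial.

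Model building concerns the random part only: "The first MLM will include a random intercept and no random slope", after which a likelihood ratio test decides whether a slope is added. No other SAP section adds a Condition × Time term, a baseline-adjusted comparison or a contrast at a named visit.

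Baseline is one of the outcome observations. SAP section 5 states: "The primary criterion of interest will be perceived stress scores, self-reported at baseline, 4-week midpoint, 8-week post, and 12-week follow-up". Protocol section II.a requires the baseline assessment to be completed before randomisation.

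The question to be answered concerns change. Protocol section I.d hypothesises that "using the Happify platform will result in greater decreases in perceived stress and rumination over an 8-week period compared to a waitlist control". The first objective in SAP section 3 is, comparing the two arms, to "examine changes in perceived stress and rumination (brooding) across baseline, 4-weeks, 8-weeks (post-intervention), and 12-weeks". Protocol section II.e planned a "2 (group: intervention vs. control) x 4 (time: baseline, 4 weeks, 8 weeks, 12 weeks) repeated-measures ANOVA" on PSS to see whether change differed between groups.

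**The concern.** In a model with Condition and Time as main effects only, both arms share one time course and differ by a constant. The between-arm difference in change, which is the hypothesis, is not a parameter of the model. The protocol's 2 × 4 ANOVA contained that test as its group-by-time interaction; the SAP lost it in moving to a multilevel model. The random slope does not bring it back. It lets individuals differ in trajectory but gives no arm-specific mean slope.

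What remains, γ01, mixes post-randomisation differences with a baseline difference that randomisation makes zero in expectation. It is neither a change nor the 8-week effect, and it is smaller than the 8-week effect whenever the benefit emerges after baseline and is then held. A chance baseline imbalance also enters the estimate directly. SAP section 5 applies the treatment comparison to all five outcomes, so the fault carries to each of them.

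**Working it through.** **Can N be used as a benchmark?** The plan gives 800 participants, 400 per arm (Protocol section III), but no alpha, power, effect size or SD, so N cannot be reproduced. For orientation, assuming two-sided 5% and 80% power, the detectable difference at one time point is (1.960 + 0.842) × √(2/400) = 0.198 SD. I therefore use d = 0.20 SD.

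**What γ01 estimates.** With complete data, a common visit covariance V and arm-difference vector δ = (δ0, δ4, δ8, δ12):

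E(γ01) = 1′V⁻¹δ / 1′V⁻¹1, with variance (2/n) / (1′V⁻¹1).

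This is a weighted average of the four visit differences. Randomisation gives δ0 = 0. The documents give no correlations, SD, effect shape or attrition rate, so the following are assumptions: total baseline variance 1, n = 400 per arm, δ = (0, 0.5d, d, d).

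*Random intercept, visit correlation 0.6.*
- Weights are 0.25 at each visit, so E(γ01) = 0.25 × (0 + 0.5 + 1 + 1)d = 0.625d.
- SE = √[0.005 × (1 + 3 × 0.6)/4] = √0.0035 = 0.0592.
- At d = 0.20, z = 0.125/0.0592 = 2.11 and power = Φ(2.11 − 1.96) = 56%.
- Week-8 contrast with a common baseline mean: SE = √[0.005 × (1 − 0.6²)] = 0.0566, z = 3.54, power 94%.
- Plain week-8 difference in change: SE = √[0.005 × (2 − 1.2)] = 0.0632, z = 3.16, power about 88%.

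*Random slope: intercept variance 0.5, slope variance 0.05 per 4-week step, residual variance 0.5.*
- Weights are 0.40/0.30/0.20/0.10, heaviest at baseline. E(γ01) = (0.30 × 0.5 + 0.20 + 0.10)d = 0.45d.
- SE = √[0.005 × 0.70] = 0.0592, z = 0.09/0.0592 = 1.52, power 33%.
- Common-baseline week-8 contrast: week-8 variance is 0.5 + 4 × 0.05 + 0.5 = 1.2 and covariance with baseline is 0.5. SE = √[0.005 × (1.2 − 0.25)] = 0.0689, z = 2.90, power 83%.
- Plain week-8 difference in change: SE = √[0.005 × (4 × 0.05 + 2 × 0.5)] = 0.0775, z = 2.58, power 73%.

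**Attrition.** SAP section 7.2 expects substantial attrition without giving a rate. I assume 20/30/35% missing at weeks 4/8/12, unrelated to outcome, and solve the same generalised least squares equations over the missingness patterns.

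| Model and data | E(γ01) | Power, SAP term | Power, common-baseline week-8 contrast |
|---|---|---|---|
| Random intercept, complete | 0.625d | 56% | 94% |
| Random intercept, visits missing independently | 0.54d | 42% | 86% |
| Random intercept, same losses as monotone dropout | 0.49d | 36% | 85% |
| Random slope, complete | 0.45d | 33% | 83% |
| Random slope, visits missing independently | 0.40d | 27% | 71% |
| Random slope, same losses as monotone dropout | 0.36d | 22% | 69% |

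**Other assumptions.** If the full effect is present from week 4, complete-data coefficients are 0.75d (random intercept) and (0.30 + 0.20 + 0.10)d = 0.60d (random slope). Across intraclass correlations of 0.3 to 0.7, slope SDs of 0 to 0.3 per visit and intercept–slope correlations of 0 or −0.3, the baseline weight runs from 0.21 to 0.52.

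**Chance imbalance.** In the random-intercept case, a baseline gap b implies an expected 0.6b at each later visit even with no effect. It therefore puts 0.25 × (1 + 3 × 0.6)b = 0.70b into γ01.

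**The case against.** The strongest defence is that the intention is clear elsewhere. The SAP objective speaks of change, the protocol planned a group-by-time design, and the equation has at least one notation slip: the random slope is printed without Time beside it, so as printed it cannot be separated from the random intercept. An analyst might well add the interaction when fitting. But the words below the equation make clear that a slope on time is meant, and nothing in the SAP does the same for an interaction. The slope notation is a side correction.

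The power figures also depend on assumptions. At intraclass correlation 0.3 with a random intercept only, the printed term has 73% power against 67% for the plain week-8 difference in change. If the full effect is also present from week 4, it has 87% against 84% even for the common-baseline contrast. So loss of power is not universal. Under no effect, the test of γ01 keeps its type I error across randomisations; the fault is dilution and the wrong estimand, not a raised false-positive rate.

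That Time is linear is inferred from its single coefficient. Regression to the mean after entry on elevated scores would affect both arms, and with complete data the coding of Time does not alter the expected Condition coefficient. It matters once an interaction is added, because prompting stops at week 8 and a straight-line divergence through week 12 may not fit.

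The usage models in section 7.3 follow a similar main-effects structure, but they are confined to the Happify arm and have no Condition term, so the dilution figures do not apply to them.

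None of this supplies the missing parameter.

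**Conclusion.** The concern holds. As written, the primary analysis sets the between-arm difference in change to zero and reports instead a visit-averaged arm difference that includes baseline. This follows from the printed model and needs no numerical assumption.

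The size does need assumptions. For an effect half present at week 4 and full at weeks 8 and 12, the coefficient is between 0.36 and 0.625 of the week-8 effect in the cases tabulated. At d = 0.20 SD and 400 per arm, power is 22% to 56%, against 69% to 94% for a common-baseline week-8 contrast. Low between-visit correlation narrows or reverses the power gap but leaves the coefficient estimating the wrong quantity. This must be corrected before the results are interpreted.

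**What to change.** Amend SAP section 7.2 so that:

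- Time is categorical (weeks 0, 4, 8, 12) and Condition × Time is in the model.
- The arms share a common baseline mean, or baseline PSS is a covariate with weeks 4, 8 and 12 as the outcomes.
- The adjusted arm difference at week 8 is the named primary contrast, with weeks 4 and 12 supportive. Week 8 matches the period in the protocol hypothesis.
- The random slope is written as u1i × Time, or replaced by an unstructured visit covariance.
- The same structure applies to brooding, optimism, sleep disturbance and loneliness.

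The interaction and the named contrast are the essential part. The baseline constraint and the covariance choice are improvements on it.

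The cost is SAP wording and a few lines of code, with no new data. SAP section 2 shows that the data had already been extracted, so the amendment should be dated and should state that it restores the group-by-time comparison in Protocol section II.e. An interaction added without record would look like a post hoc choice.
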